14.3.2 Safety Analyses

All safety data will be populated in the individual CRFs. All safety data will be listed by subjects.

Dosing dates and times will be listed by subject.

AEs will be coded using the Medical Dictionary for Regulatory Activities (MedDRA[®]) and summarized by treatment for the number of subjects reporting the TEAE. A by-subject AE data listing including verbatim term, coded term, treatment, severity, and relationship to treatment will be provided.

Safety data including ECGs, physical examinations, glucose monitoring, vital signs assessments, clinical laboratory results, will be summarized by treatment and point of time of collection.

Descriptive statistics using appropriate summary statistics will be calculated for quantitative safety data as well as for the difference to baseline, when appropriate.

Concomitant medications will be listed by subject and coded using the WHO drug dictionary. Medical history will be listed by subject.

15 STUDY ADMINISTRATION

15.1 Ethics

15.1.1 Institutional Review Board

This protocol will be reviewed by the Advarra IRB, and the study will not start until the IRB has approved the protocol or a modification thereof. The IRB is constituted and operates in accordance with the principles and requirements described in the US Code of Federal Regulations (21 CFR Part 56). The IRB is compliant to International Council for Harmonisation (ICH) guidelines, and may be reached at:

Advarra IRB
[name]
[name]
[contact]

15.1.2 Ethical Conduct of the Study

This research will be carried out in accordance with the protocol, US Code of Federal Regulations, 21 CFR Parts 50, 56, and 312, the ethical principles set forth in the Declaration of Helsinki, GCP, and the ICH harmonized tripartite guideline regarding GCP (E6[R2] Good Clinical Practice: Integrated Addendum to E6 [R1], March 1st 2018).

15.1.3 Subject Information and Consent

The purpose of the study, the procedures to be carried out and the potential hazards will be described to the subjects in non-technical terms. Subjects will be required to read, sign and date an ICF summarizing the discussion prior to screening, and will be assured that they may withdraw from the study at any time without jeopardizing their medical care.

Subjects will be given a copy of their signed ICF.

15.1.4 Confidentiality

All members of the Investigator's staff have signed confidentiality agreements with Celerion. By signing this protocol, the Investigator and Celerion staff will regard all information provided by the Sponsor and all information obtained during the course of the study as confidential.

The Investigator must guarantee the privacy of the subjects taking part in the study. Subjects will be identified throughout documentation and evaluation by a unique subject study number. Throughout the study, a subject's source data will only be linked to the Sponsor's clinical study database or documentation via a unique identification number. If subject name appears on any study document, it must be redacted before the copy of the documents is supplied to the Sponsor. Any information concerning the subjects (clinical notes, identification numbers, etc.) must be kept on file by the Investigator who will ensure that it is revealed only to the Sponsor, IRB, or regulatory authorities for the purposes of trial monitoring, auditing or official

inspections. As required, in the case of an event where medical expenses are the responsibility of the Sponsor, personal information i.e., full name, social security details etc., may be released to the Sponsor. Appropriate precautions will be taken to maintain confidentiality of medical records and personal information in strictest confidence and in accordance with local data protection laws.

15.2 Termination of the Study

Celerion reserves the right to terminate the study in the interest of subject welfare.

Sponsor reserves the right to suspend or terminate the study at any time.

15.3 Data Quality Assurance

Standard operating procedures are available for all activities performed at Celerion relevant to the quality of this study. Designated personnel of Celerion will be responsible for implementing and maintaining quality assurance (QA) and quality control systems to ensure that the study is conducted, and that data are generated, documented and reported in compliance with the study protocol, GCP and GLP requirements as well as applicable regulatory requirements and local laws, rules and regulations relating to the conduct of the clinical study.

The Clinical Study Report will be audited by the QA department and the QA audit certificate will be included in the study report.

All clinical data will undergo a 100% quality control check prior to clinical database lock. Edit checks are then performed for appropriate databases as a validation routine using SAS® or comparable statistical program to check for missing data, data inconsistencies, data ranges, etc. Corrections are made prior to database lock.

15.4 Direct Access to Source Data/Documents

Celerion will ensure that the Sponsor, IRB, and inspection by domestic and foreign regulatory authorities will have direct access to all study-related sites, source data/documents, and reports for the purpose of monitoring and auditing (ICH[E6] 5.1.2 & 6.10). In the event that other study-related monitoring should be done by other parties, they will be required to sign a confidentiality agreement prior to any monitoring and auditing.

15.5 Drug Supplies, Packaging and Labeling

The Sponsor will supply sufficient quantities of the LOXO-292 capsules to allow completion of this study. Celerion will provide sufficient quantities of repaglinide and chewable glucose tablets to allow completion of the study. The lot numbers and expiration dates (where available) of the study drugs supplied will be recorded in the final Clinical Study Report.

Records will be made of the receipt and dispensing of the study drugs supplied. At the conclusion of the study, any unused study drugs will be retained by Celerion, returned to the Sponsor or designee, or destroyed, as per Sponsor instructions. Any remaining supplies that

were purchased by Celerion will be destroyed. If no supplies remain, this fact will be documented in the pharmacy product accountability records.

15.6 Data Handling and Record Keeping

Celerion standard CRFs will be supplied. CRFs are produced and may be printed off from the database and made available to the designated study team members. The CRFs are also stored electronically. Each CRF book is reviewed and signed by the PI. The final signed CRFs are provided to the Sponsor on CD.

All raw data generated in connection with this study, together with the original copy of the final Clinical Study Report, will be retained by Celerion until at least 2 years after the last approval of a marketing application in an ICH region and until there are no pending or contemplated marketing applications in an ICH region or at least 5 years have elapsed since the formal discontinuation of clinical development of the investigational product. These documents should be retained for a longer period however if required by the applicable regulatory requirements or by an agreement with the Sponsor. It is the responsibility of the Sponsor to inform the PI/Institution as to when these documents no longer need to be retained.

15.7 Report Format

According to the ICH Harmonized Tripartite Guideline (Organization of the Common Technical Document for the Registration of Pharmaceuticals for Human Use M4 and the ICH M2 Expert Working Group), the final Clinical Study Report will be written according to the ICH E3 Guideline (Structure and Content of Clinical Study Reports).

15.8 Publication Policy

All unpublished information given to Celerion by the Sponsor shall not be published or disclosed to a third party without the prior written consent of the Sponsor.

The data generated by this study are considered confidential information and the property of the Sponsor. This confidential information may be published only in collaboration with participating personnel from the Sponsor or upon Sponsor's written consent to publish the article.

1. INTRODUCTION

The following statistical analysis plan (SAP) provides the framework for the summarization of the data from study LOXO-RET-18026. The SAP may change due to unforeseen circumstances. Any changes made from the planned analysis within the protocol or after the locking of the database will be documented in the clinical study report (CSR). The section referred to as Table Shells within this SAP describes the traceability of the tables, figures, and listings (TFLs) back to the data. Note that the header for this page will be the one used for the main body of the CSR.

Any additional exploratory analyses not addressed within this SAP and/or driven by the data, or requested by Loxo Oncology, Inc., will be considered out of scope and will be described in the CSR as needed.

2. OBJECTIVES AND ENDPOINTS

2.1 Objectives

Primary:

To investigate the effect of multiple-dose LOXO-292 on the single-dose pharmacokinetics (PK) of repaglinide, a sensitive cytochrome P450 (CYP) 2C8 (CYP2C8) substrate, in healthy adult subjects.

Secondary:

1. To evaluate the single-dose PK of LOXO-292 administered alone and the multiple-dose PK of LOXO-292 with coadministration of repaglinide in healthy adult subjects.
2. To determine the safety and tolerability of multiple-dose LOXO-292 with and without coadministration of repaglinide in healthy adult subjects.

2.2 Endpoints

Pharmacokinetics:

The following PK parameters will be calculated for repaglinide in plasma in Period 1, **CCI** and Period 2, **CCI**: AUC0-t, AUC0-inf, AUC%extrap, Cmax, Tmax, Kel, t_{1/2}, CL/F, and Vz/F.

The following PK parameters will be calculated for LOXO-292 in plasma in Period 2, on Day 1 (following morning dosing): AUC0-12, AUC0-t, Cmax, and Tmax; and on Day 10 (following morning dosing): AU τ , Cmax,ss, Tmax,ss, and CL,ss/F. Additionally, C_{trough} values will be assessed following the 2nd dose on **CCI**

CCI

Safety:

Safety endpoints will include 12-lead ECGs, physical examinations, vital signs, glucose monitoring, clinical laboratory tests, and AEs.

3. STUDY DESIGN

This is an open label, 2-period, fixed-sequence study.

Sixteen (16), healthy, adult male and female (women of non-childbearing potential only) subjects will be enrolled. Every attempt will be made to enroll at least 3 subjects of each sex.

Screening of subjects will occur within 28 days prior to the first dosing (i.e., repaglinide).

In Period 1, Day 1, a single oral dose of repaglinide will be administered. PK samples for repaglinide will be collected predose and for 16 hours postdose.

In Period 2, oral doses of LOXO-292 will be administered twice daily (BID) for 10 consecutive days (Days 1 to 10). The single dose of repaglinide will be coadministered with the single dose of LOXO-292 on the morning of Day 10. PK sampling for repaglinide will be collected predose and for 16 hours following repaglinide dosing on Day 10. PK sampling in plasma for LOXO-292 will be collected CCI

In both periods, glucose will be administered immediately following repaglinide dosing on Day 1 of Period 1 and Day 10 of Period 2 and additionally, at approximately 1 hour postdose on Day 10 of Period 2.

There will be a washout period of 24 hours between the repaglinide dose in Period 1 and the first LOXO-292 dose in Period 2.

Safety and tolerability will be assessed through End of Treatment (EOT) or early termination (ET) by monitoring AEs, performing physical examinations, glucose monitoring, and clinical laboratory tests, measuring vital signs, and recording ECGs.

Subjects will be permitted to be replaced at the discretion of the Sponsor.

Subjects will be housed through EOT or ET beginning in Period 1, Day -1, at the time indicated by the clinical research unit (CRU), until after completion of study procedures in Period 2, Day 11 (EOT) or ET study procedures.

The CRU will contact all subjects who received at least one dose of study drug (including subjects who terminated the study early [ET]) at the End of Study (EOS) by a follow up (FU) phone call. The EOS/FU phone call will be performed 7 ± 2 days after the EOT visit or ET visit to determine if any SAE or study drug related AE has occurred since the EOT or ET visit.

4. ANALYSIS POPULATIONS

4.1 Analysis Populations

Safety Population

All subjects who received at least one dose of either of the study drugs will be included in the safety evaluations.

Pharmacokinetic Population

Samples from all subjects will be assayed even if the subjects do not complete the study. All subjects who comply sufficiently with the protocol and display an evaluable PK profile (e.g., exposure to treatment, availability of measurements and absence of major protocol violations) will be included in the statistical analyses.

Data for each subject will be included in the summary statistics and statistical comparisons of PK parameters with the exceptions described as follows:

- Data from subjects who experience emesis at or before 2 times median Tmax for the given treatment during the PK sampling period time course of the study for repaglinide and LOXO-292 may be excluded from the summary statistics for the given treatment and from the statistical comparison of PK parameters.
- Data from subjects who significantly violate a protocol inclusion or exclusion criterion, deviate significantly from the protocol, or have unavailable or incomplete data that may influence the PK analysis will be excluded from the PK Population.

Any subject or data excluded from the analysis will be identified, along with their reason for exclusion, in the CSR.

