11.4.2 Meals

Water (except water provided with each dosing) will be restricted 1 hour prior to and 1 hour after each study drug administration, but will be allowed ad libitum at all other times. Other fluids may be given as part of meals and snacks but will be restricted at all other times throughout the confinement period.

In Period 1, Day 1, subjects will fast overnight for at least 10 hours prior to study drug administration and will continue to fast for at least 4 hours postdose.

In Period 2, Days 1 to 9 and for the evening dose on Day 10, subjects will fast for at least 2 hours prior to each dose (morning and evening, as appropriate) and will continue the fast for at least 1 hour postdose.

In Period 2, Day 10 morning dose, subjects will fast overnight for at least 10 hours prior to study drug administration and will continue to fast for at least 4 hours postdose.

When confined, standard meals and snacks will be provided at appropriate times, except when they are required to fast. When confined in the CRU, subjects will be required to fast from all food and drink except water between meals and snacks.

Each meal and/or snacks served at the CRU will be standardized and will be similar in caloric content and composition and will be taken at approximately the same time in each period.

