13.2.5 Glucose Monitoring

13.2.5.1 Blood Glucose

Blood glucose determinations will be performed as outlined in the Study Events Flow Chart ([Section 6](#)).

All measurements will be done with a glucose monitor and will be performed by finger stick.

Subjects who manifest hypoglycemic symptoms such as faintness, sweatiness, tachycardia, and headache, may have their blood glucose monitored by finger stick at any time during the study, at the discretion of the PI. In addition, the PI or designee may administer additional oral glucose, 16 g of glucose (4 x 4 g chewable tablets), if the blood glucose (monitored by finger stick) at any of the specified time points is < 60 mg/dL or at any other time based on evaluation of symptoms. For subjects with blood glucose < 60 mg/dL, intervention measurements outlined in protocol [Section 13.2.5.2](#) will be followed.

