13.2.5.2 Rescue Intervention for Hypoglycemia

The following steps may be followed at the discretion of the PI:

The subject should be placed in a semi recumbent position. A conscious subject who is safely able to take food/drink by mouth should ingest 15-20 g of glucose. A glucose measurement should be taken 15 minutes later. If hypoglycemia persists, the treatment should be repeated.

Once the blood glucose concentration exceeds 70 mg/dL, the subject should consume a full meal containing at least 60 g of carbohydrate.

Following administration of food, blood glucose concentrations should be measured every 10-15 minutes for the first hour, every 30 minutes for an additional 2 hours, then hourly until blood glucose concentrations have been demonstrated to be stable within the normal range for at least 3 hours and, if present, symptoms have resolved. Oral supplementation may be attempted up to three times prior to intervention with intravenous (IV) dextrose. If a subject displays any signs/symptoms of instability, in the opinion of the PI, IV dextrose will be used immediately. If oral glucose and IV dextrose cannot be administered in an emergency situation, intramuscular glucagon will be used.

Subjects will be offered placement of an IV catheter in the event that dextrose is required. The IV catheter should be placed on the opposite arm from which the PK blood draws are taken.

If subject remains hypoglycemic and there has been no resolution of any associated symptoms despite the interventions described above, the subject should be rapidly transferred to a location where definitive care (i.e., an Emergency Room or Intensive Care Unit) is available.

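### Does SAP 4.1 need a rule for a hypoglycemia rescue meal eaten inside the 4-hour fast after repaglinide?

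*SAP*

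**What the plan says.** SAP 4.1 has one event-specific rule, for emesis: such data "may be excluded from the summary statistics for the given treatment and from the statistical comparison of PK parameters". Everything else falls under a general rule, by which data from subjects who "deviate significantly from the protocol, or have unavailable or incomplete data that may influence the PK analysis will be excluded from the PK Population". The word significantly is not defined, and rescue, meals and broken fasts are not mentioned. The section closes by requiring that any subject or data left out be identified in the study report with the reason.

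On eating, Protocol 11.4.2 says that on both repaglinide days subjects "will continue to fast for at least 4 hours postdose". On rescue, Protocol 13.2.5.2 opens with "The following steps may be followed at the discretion of the PI". It then gives the oral step and its recheck: "A glucose measurement should be taken 15 minutes later. If hypoglycemia persists, the treatment should be repeated". The meal follows: "Once the blood glucose concentration exceeds 70 mg/dL, the subject should consume a full meal containing at least 60 g of carbohydrate". The limit on the oral route is that "Oral supplementation may be attempted up to three times prior to intervention with intravenous (IV) dextrose". Protocol 13.2.5.1, by contrast, says these measures will be followed when glucose is below 60 mg/dL.

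**The concern.** A meal given under 13.2.5.2 before 4 hours follows one protocol section and breaks another. If the breach is significant, SAP 4.1 requires exclusion. If it is authorised care, the subject stays. Nothing settles this before repaglinide concentrations are known.

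The event was foreseeable. The Protocol Revision History records four subjects below 60 mg/dL in Period 1, and glucose checks inside the fast rise from two in Period 1 to five on Day 10 of Period 2.

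Both handlings of a Treatment B meal could also pull the B/A ratio down, in a study looking for an increase. Keeping the subject may lower B, because Protocol 8.1.2 reports that food reduces repaglinide Cmax by 20% and AUC by 12.4%. Dropping subjects who were rescued because their exposure was high removes large B values.

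Finally, the emesis rule is discretionary and tied to one treatment, whereas the deviation rule refers to the whole PK Population. On a literal reading, a Day 10 meal could cost a subject's Period 1 data and LOXO-292 troughs.

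**Working it through.** The plan states no figure to reproduce: Protocol 14.1 gives 16 subjects without a CV or precision target. All CVs below are assumptions.

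**1. When would the meal fall?** Inputs: check times from SAP Table 7.5; a 15-minute recheck and one to three oral attempts from Protocol 13.2.5.2. Earliest meal time = check time + 0.25 h × attempts.

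| Period | Check (h) | Meal (h) |
|---|---|---|
| 1 | 1 | 1.25–1.75 |
| 1 | 2 | 2.25–2.75 |
| 2 | 0.5 | 0.75–1.25 |
| 2 | 1 | 1.25–1.75 |
| 2 | 1.5 | 1.75–2.25 |
| 2 | 2 | 2.25–2.75 |
| 2 | 3 | 3.25–3.75 |

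All seven ranges lie inside the fast, but only if glucose exceeds 70 mg/dL at one of those rechecks and the meal is eaten at once. The protocol guarantees neither. A rescue begun before 4 h is compatible with the fast if glucose recovers after 4 h, if the meal comes later, or if the investigator uses the stated discretion.

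**2. Subject kept.** Let k of 16 subjects eat early in Treatment B only and feel the whole food effect. The ratio is multiplied by (1 − 0.124)^(k/16) for AUC and (1 − 0.20)^(k/16) for Cmax.

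- k = 1: 0.876^(1/16) = 0.992; 0.80^(1/16) = 0.986.
- k = 4: 0.876^(4/16) = 0.967; 0.80^(4/16) = 0.946.

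These are extremes. The food figures are for repaglinide given with food, and Protocol 8.1.2 puts Tmax within 1 h. Of the 21 check-and-attempt combinations (7 × 3), only two, at 0.75 and 1.0 h, give a meal at or before 1 h. If the meals fall in Treatment A instead, the factors invert: for k = 4, 1/0.967 = 1.034 and 1/0.946 = 1.057.

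**3. Subject excluded.** Suppose the k highest Treatment B exposures are dropped. The multiplier is exp(−m·sw²/√(sb² + sw²)), where sw² and sb² are the within- and between-subject variances, ln(1 + CV²), and m is the drop in the mean of 16 standard normals when the top k are removed (0.117 for k = 1, 0.399 for k = 4).

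- Between/within CV 50%/30%: sb² = 0.2231, sw² = 0.0862, so sw²/√(sb² + sw²) = 0.155. k = 1: exp(−0.117 × 0.155) = 0.982. k = 4: exp(−0.399 × 0.155) = 0.940.
- k = 4 at other CVs: 0.977 (70%/20%) and 0.885 (30%/40%, an extreme case).
- Rescue unrelated to exposure: 1.00.

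**4. Precision.** The 90% CI runs from the ratio divided by F to the ratio times F, with F = exp(t(0.95, n−1) × sw × √(2/n)). At CV 30% and complete pairs, F = 1.200 for n = 16, 1.208 for n = 15 and 1.240 for n = 12.

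**5. How large is k?** Unknown. Four of 16 planned subjects is 25% (Clopper–Pearson 95% CI 7% to 52%). Those were low readings, not meals, in Period 1 after 12 g of glucose. Day 10 of Period 2 provides 16 g twice. The Revision History says values recovered after lunch and gives no time for it.

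**6. What would exclusion remove?** SAP 4.1 speaks of data from subjects, and then of any subject or data excluded, so leaving out only the affected profile is open to the analyst. By SAP Table 6.3 the last trough is the Day 10 predose sample, which precedes any Day 10 meal. There is no pharmacokinetic reason to discard the troughs.

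**The case for a change.** The strongest case for a change is that it is cheap and that disclosure is not prespecification. The SAP already carries the amended glucose schedule, so it was written with the hypoglycemia known. The trial is open-label, and the keep-or-drop choice could be made after concentrations are seen. A few sentences and one conditional rerun of the planned model would remove that freedom. The general rule in Protocol 13 giving urgent safety procedures precedence does not say how the PK profile is then classified.

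Part of this stands. The classification is unwritten. Protocol 11.4.2 and 13.2.5.2 do conflict when the meal is given promptly and glucose exceeds 70 mg/dL before 4 h. Protocol 13.2.5.1 and 13.2.5.2 differ on whether the steps are obligatory. The sponsor has to reconcile these passages; which reading should prevail is not a statistical question.

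The rest is weaker. The two sections are not incompatible for every early rescue. Loss of Period 1 data and troughs is one reading of SAP 4.1, not its stated consequence. The downward bias on exclusion needs rescue to track high repaglinide exposure, which no section shows for these subjects. The added text would gain little, because it would leave the keep-or-exclude decision to be made later and add only a second run.

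**Conclusion.** No change to the SAP follows. This is missing detail about a conditional event, which analysts can fill sensibly under the existing rules. They can judge whether a meal given as protocol rescue is a significant deviation, limit any exclusion to the affected profile, and report it. The result would be open to checking: the SAP lists deviations (Appendix 16.2.2), PK exclusions (16.2.3), glucose times (16.2.5.4.3) and meal times (16.2.5.6). SAP 6.6 keeps excluded subjects in the individual PK parameter tables, so a reader can recompute the B/A ratio with and without them.

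The size supports this. One affected subject moves the ratio by under 2% either way (0.992 for AUC or 0.986 for Cmax if kept, 0.982 if dropped). Four give at most 0.967 and 0.946 if kept, and 0.940 if dropped at assumed CVs of 50% and 30%, with a range of 0.885 to 1.00 across the other assumptions. At CV 30% the 90% CI already spans a factor of 1.200 each way with all 16 subjects.

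These figures assume that all the meals fall in Treatment B, that the full with-food effect applies if subjects are kept, and, for values below 1.00 on exclusion, that rescue follows high exposure. No meal inside the fast is documented, and the effect may be nil.
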